6.3 Per Protocol Analysis Set (PPS)

The Per Protocol Analysis Set (PPS) contains all subjects in the Full Analysis Set who have no major protocol deviations that impacting the effectiveness endpoint. PPS will be used for effectiveness analyses.

6.4 Safety Analysis Set (SAF)

The Safety Analysis Set (SAF) contains all subjects who provide informed consent and have MW ablation attempted with the NeuWave system and includes run-in phase subjects. The Safety Set will be used for summarization of safety endpoints only.

6.5 Run-in Analysis Set

The Run-in analysis set contains all subjects participating in the run-in phase.

7 Sample Size Justification

The total sample size will be 137 subjects. This includes 3 patients at each site (12 patients across 4 sites) who will be part of the run-in phase. There are no stated hypotheses in this study from which a power calculation and sample size determination will be performed; rather, a minimum of 100 subjects providing data to at least 1 year is determined to be sufficient to provide an evaluation of safety and effectiveness of the NeuWave Certus Microwave Ablation System. In anticipation of up to 20% dropout, a total of 125 subjects will be enrolled after completion of the run-in phase for a total of 137 subjects.

8 Analyses to be Conducted

8.1 General Conventions

8.1.1 Reference Start Dates

Reference start date is defined as the day of subjects undergoing first microwave ablation, considered as Day 0 (Day 1 is the next day of the first microwave ablation) and appear in every listing where an assessment date or event date appears.

8.1.2 Study day

The onset day of AE is calculated from the date of first microwave ablation administrated to the date of the AE start date, as follows:

Onset Day = (date of event - date of first microwave ablation + 1) if date of event happens on or later than date of ablation.

Onset Day = (date of event – date of first microwave ablation) if date of event happens earlier than date of ablation.

Study Day will be calculated from the reference start date (date of first microwave ablation) and will be used to show start/stop day of assessments and events.

Study Day = (date of event – date of first microwave ablation + 1) if date of event happens on or later than date of ablation

Study Day = (date of event – date of first microwave ablation) if date of event happens earlier than date of ablation.

In the situation where the event date is partial or missing, the Onset Day/Study Day and any corresponding durations will appear missing.

If a date is partial, no imputation will be done except for adverse events (AEs). If the day of AE start is missing, the first day of the month is considered as the start date, unless the month is the same month as the month of ablation, in which case day will be set equal to the day of ablation. If month part is missing, the AE start date is imputed as the first day of the year, unless the same year of ablation, in which case day will be set equal to the day of ablation. If the day or month of AE end is missing, the day will be imputed as the end day of the month or the year, unless the same month or year as the day of ablation. If the imputed date happens later than death date, the date is replaced with death date.

Based on the protocol, there will be no imputation of missing data for any parameters or for early terminated patients.

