06 AUGUST 2020, VERSION: 4.0

- Length of hospital stay.
- Complete tumor ablation evaluation.
- Any update to relevant concomitant medications.
- Relevant concomitant procedures.
- All AEs and SAEs.

Post Ablation Follow-up Visits 3 to 11 (End of Study)

The following data will be collected post ablation at the post ablation follow-up visits, from Visit 3 through the end of the study (Visit 11), as follows:

- Pain score, using the NPRS (Visit 3 only).
- Quality of Life questionnaires: NPRS pain score, EORTC QLQ-C30 and liver-specific EORTC QLQ-HCC18.
- MRI of the liver.
- Laboratory tests.
 - Coagulation tests (PT, APTT, and INR).
 - Liver function tests (AST, ALT, GGT, albumin, indirect, direct and total bilirubin, and total protein).
 - o Renal function test (Urea, creatinine, and electrolytes [sodium, potassium, and chloride]).
 - Complete blood count (differential cell count and platelet count).
 - Alpha-fetoprotein (AFP) test.
- ECOG performance status.
- Complete tumor ablation evaluation (Visit 3 only)
- Local tumor progression (LTP) to be evaluated by a study physician based on MRI imaging. All MRI scans are to be submitted to the Sponsor.
- Progression-free survival to be evaluated by a study physician based on MRI imaging or may be reported by a patient's primary treating oncologist, if different than the study physician. If there is a progression, the study physician should specify if the progression is of the original target tumor, a new HCC tumor in the liver, or a distant metastasis.
- Any update to relevant concomitant medications.
- Relevant concomitant procedures.
- All AEs (if within 30 days post an ablation procedure).
- All SAEs through end of study.

Confidential Page 39 of 61 06 AUGUST 2020, VERSION: 4.0

Note: Repeat ablations may be performed on target tumor(s) only.

Unscheduled Visits

The following data will be collected at all unscheduled visits:

- Reason for the unscheduled visit.
- Relevant concomitant medications.
- Relevant concomitant procedures.
- AEs (if within 30 days post an ablation procedure) and all SAEs.

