8.1.6 Cut-off conventions

All available data will be included at the time of the cut-off date. Missing or partial dates (unable to compare) will also be presented, but no imputation for any date will occur except for partial adverse event dates as described in section *8.1.2*.

Adverse events and concomitant medications with no end date available by the cut-off date will be considered as ongoing events. If the start date is prior to / on the cutoff date, the end dates will be presented regardless if the end dates are post cut-off date or not. Ongoing events will be summarized for analysis using the cut-off date as the date of completion, with an indication that event is ongoing.

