	Local Tumor Progression and over one missed tumor assessment prior to confirmed	Date of the latest evaluable local tumor assessment prior to the missed	
B2	LTP	assessment	Event
		Date of last local	
		tumor assessment	
	No progression, either alive or	with no documented	
С	death	LTP	Censored

Table 3: Censoring Rules for LTP

		Date of last tumor assessment with no documented	
D	Dead	progression	Censored
		Date of last tumor	
		assessment with no	
		documented	
E	Withdrawal by Subject	progression	Censored

Local tumor progression rates at 3, 6, 9, 12, 18, 24, 30, and 36 months will be estimated using the Kaplan-Meier (K-M) method and 95% confidence intervals (Greenwood's formula) will be provided.

The K-M curve of time to LTP will be provided.

Secondary efficacy rate (the 2nd interim, final)

Secondary efficacy rate is defined as the percentage of subjects whose tumors have undergone successful repeat ablation following identification of local tumor progression at any time during study follow up.

It could be found in CRF page, Ablation Zone Assessment, "Re-ablate with Neuwave". For subgroup that has LTP and used Certus to re-ablate, the number and percentage of subjects achieving secondary efficacy, will be summarized and a 95% confidence interval will be estimated using wald method.

Progression-free survival (PFS) (the 2nd interim, final)

PFS is defined as length of time from initial ablation until disease progression.

Table	e 4. Censoring Rules for PFS		
	Situation	Event Date	Outcome
No po	st-baseline or no baseline Ablation Zo	ne Assessment	
	No post-baseline tumor evaluation		
A1	and alive	Date Ablation performed	Censored
	No post-baseline tumor evaluation		
	but died on or before the second		
A2	scheduled tumor assessment	Date Ablation performed	Censored
With baseline and post-baseline tumor assessments			

Table 4: Censoring Rules for PFS

В	Any Tumor Progression and zero or one missed tumor assessment prior to progression	Date of first progression	Event
		Date of last progression	
	PD happens after >=2 consecutively	assessment before	
С	missing tumor assessment	missing assessments	Censored
		Date of last progression	
		assessment with no	
D	No progression	documented progression	Censored

Progression-Free Survival rate will be estimated using the Kaplan-Meier method and 95% confidence intervals (Greenwood's formula) will be provided for 6, 12, 18, 24, 30, 36 months.

The K-M curve of time to progression will be provided.

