Progression-free survival (PFS) sensitivity analysis (the 2nd interim, final)

PFS is defined as length of time from initial ablation until disease progression or death, whichever comes first.

Overall survival (OS)

36-month OS is measured from the time of the first ablation procedure to the time of death or last follow-up, if death has not occurred.

For OS, death from any cause will be considered as an event. If no death is reported, then use the cut-off date as the censored date of OS.

Overall Survival rate will be estimated using the Kaplan-Meier method and 95% confidence intervals (Greenwood's formula) will be provided.

The K-M curve of time to death will be provided.

Quality of Life (QoL)

EORTC QLQ-C30

The EORTC QLQ-C30 (version 3.0) comprises 30 questions and provides a multidimensional assessment of QoL. The QLQ-C30 is composed of both multi-item scales and single-item measures. EORTC QLQ-C30 can be combined to produce 5 functional scales (Physical, Role, Cognitive, Emotional, and Social), 3 symptom scales (Fatigue, Pain, and Nausea/vomiting), 5 individual items (dyspnea, insomnia, appetite loss, constipation, and diarrhea) and a global measure of health status. Each of the multi-item scales includes a different set of items - no item occurs in more than one scale. All of the scales and single-item measures range in score from 0 to 100. A high scale score represents a higher response level.

There are four items for each question (from Q1 to Q28): from not at all, a little, quite a bit, to very much, each will be considered as from 1 to 4. For Q29 and Q30, will be scored from 1 to 7.

No response (NR) will not be considered as missing and not included in the analysis.

Scale	Number of items	ltem range*	Item numbers
Global health status / QoL			
Global health status/QoL	2	6	29, 30
Functional scales			
Physical functioning	5	3	1 to 5
Role functioning	2	3	6, 7
Emotional functioning	4	3	21 to 24
Cognitive functioning	2	3	20, 25
Social functioning	2	3	26, 27
Symptom scales / items			
Fatigue	3	3	10, 12, 18
Nausea and vomiting	2	3	14, 15
Pain	2	3	9, 19
Dyspnoea	1	3	8
Insomnia	1	3	11
Appetite loss	1	3	13
Constipation	1	3	16
Diarrhoea	1	3	17
Financial difficulties	1	3	28

Table 5: Scoring the EORTC QLQ-C30 version 3.0

* *Item range* is the difference between the possible maximum and the minimum response to individual items; most items take values from 1 to 4, giving *range* = 3.

The scoring procedure is as follows:

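### SAP 8.1.2 and 8.1.6 leave a known death or progression with an incomplete date without a survival time, and no fallback is given for the Kaplan-Meier OS and PFS estimates

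*SAP*

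**What the plan says.** **Date rules.** SAP 8.1.2, after the onset-day and study-day formulas, states: "In the situation where the event date is partial or missing, the Onset Day/Study Day and any corresponding durations will appear missing". It then makes adverse events the only exception to a ban on imputing partial dates, and its last sentence repeats the protocol's ban on imputing missing data for any parameter. SAP 8.1.6 says that "no imputation for any date will occur except for partial adverse event dates". SAP 8.7 and protocol 8.6 also rule out imputation and make no exception for event dates.

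**Endpoints.** In SAP 8.4.1, OS is "measured from the time of the first ablation procedure to the time of death" or last follow-up. "For OS, death from any cause will be considered as an event". The censoring rule is: "If no death is reported, then use the cut-off date as the censored date of OS". For the main analysis, "PFS is defined as length of time from initial ablation until disease progression"; death is not an event. The PFS sensitivity analysis adds death as an event.

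**Source of progression dates.** Protocol 7.2.4 has a study physician assess progression on MRI, but it also says that progression "may be reported by a patient's primary treating oncologist", where that is a different person.

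**The concern.** OS and PFS times are differences between two dates. If the second date is incomplete and may not be completed by rule, the patient is a known event with no time, and a Kaplan-Meier estimate cannot use such a record. The programmer would have to drop it, censor it or devise a rule after seeing the data.

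The exposure is one-sided. A patient without an event is censored at a cut-off, visit or assessment date, which is normally complete. Only events can be lost, so the curve can only move up. In a single-arm study intended to support registration (protocol 4.3), no control arm shares the shift. With no acceptance criterion set (protocol 8.4), the survival estimates themselves are what will be compared with other therapies.

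**Working it through.** **Step 1. Is there a fallback?** Each rule that might supply a date, applied to a death known only to the month:

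| Rule | Covers it? |
|---|---|
| SAP 8.1.2, AE date imputation | No. It is not linked to the death date used for OS, and protocol 14.2 does not have deaths from progressive disease reported as SAEs. It also caps imputed AE dates at the death date, so it presupposes one. |
| SAP 8.1.5, last contact date | No. Derived only for subjects not known to have died. |
| SAP 8.4.1, OS censoring at cut-off | No. Applies only where no death is reported. |
| Protocol 8.6, censoring at last visit in the final analysis | No. Applies only to patients without an event. |

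For a progression with an incomplete date, SAP Table 4 has rows for no progression, for progression with at most one missed assessment, and for progression after two or more consecutive missed assessments. It has none for an incomplete progression date.

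**Step 2. Which endpoints are exposed?**
- OS: any death with a partial date.
- PFS sensitivity analysis: such a death, if no dated progression came first; also a progression without a full date.
- Main PFS: only a progression without a full date. Deaths are not events there.

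**Step 3. Inputs for an illustration.**
- The plan's sample size reproduces: 100 / (1 − 0.20) = 125, plus 4 × 3 = 12 run-in patients, gives 137. The Full Analysis Set excludes run-in, so take n = 125.
- Three-year OS of 72.5%, from the background study in protocol 4.1.1. Using it here is an assumption.
- Complete 36-month follow-up (assumed for the simple calculation).
- Number of deaths lost, k: not given in the documents, so shown for 1 to 3.

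**Step 4. Size for OS.**
- Deaths: 125 × (1 − 0.725) = 34.4, taken as 34.
- OS with all deaths counted: 91/125 = 72.8%.
- 95% CI half-width: 1.96 × √(0.728 × 0.272 / 125) = 7.8 points.
- OS with k deaths removed: 91 / (125 − k).

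| k lost | 36-month OS | Shift (points) |
|---|---|---|
| 0 | 72.8% | – |
| 1 | 91/124 = 73.4% | +0.6 |
| 2 | 91/123 = 74.0% | +1.2 |
| 3 | 91/122 = 74.6% | +1.8 |

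With n = 100 (28 deaths, OS 72.0%), the shifts for k = 1, 2 and 3 are +0.7, +1.5 and +2.2 points.

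**Step 5. Check with dropout.** In simulated Kaplan-Meier estimates (125 patients, exponential survival with 72.5% at 36 months, 20% dropout, 1,500 runs per setting), about 31 deaths are observed on average. If 5% of deaths are lost (mean 1.5), mean OS goes from 72.5% to 73.5%. If 10% are lost (mean 3.1), it goes from 72.4% to 74.5%. Censoring those deaths at the preceding visit gives 73.6% and 74.7%, so that choice does not remove the bias. The 5% and 10% are assumptions.

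**The case against.** The strongest reply is that this is an unstated derivation rule, not a plan to discard deaths. The sentence on missing durations sits in a study-day section and can be read as a listing convention; SAP 8.4.1 never refers to it. That stands as far as it goes: neither document says that such patients leave the analysis, and exclusion is an inference. But SAP 8.1.6 extends the ban to any date other than a partial AE date, and SAP 8.4.1 supplies nothing in its place, so the gap remains on either reading.

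Practical safeguards also count. Protocol section 9 has missing data queried, deaths have their own CRF page (SAP 8.5.2), and most progressions will be dated by a scheduled MRI. The number of incomplete dates should be small, although a query cannot recover a day that nobody knows. No hypothesis or threshold is set, so no formal decision would change.

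Three stronger readings are tempting and should not be drawn:
- **That such a patient would be censored at the cut-off as alive.** SAP 8.4.1 uses the cut-off only when no death is reported, and here one is.
- **That incompletely dated deaths bias every survival endpoint.** They cannot affect main PFS.
- **That many dates will be partial.** The documents give no rate, and nothing in them says that oncologist-reported progressions lack a day.

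**Conclusion.** The gap is real and modest. The SAP addresses partial dates, exempts only adverse events, and leaves a known death or progression with an incomplete date without a usable time. Any resulting loss raises the survival estimate. The exposure is mainly in OS and the death-counting PFS sensitivity analysis; for main PFS it is confined to progressions without a full date, such as some reported by an outside oncologist, and no size is estimated for it.

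For OS the shift is about 0.6 point per lost death, or 0.6 to 1.8 points for 1 to 3 deaths, well inside a CI half-width of about 7.8 points. This rests on 125 patients, complete follow-up, the cited 72.5% three-year OS and an assumed count of lost deaths. The case for acting is that the error has one direction, the handling would otherwise be chosen after the data are seen, and the remedy is cheap.

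**What to change.** State in SAP 8.1.2 and 8.4.1 that no known death or progression is excluded or censored because its date is incomplete, and pre-specify how the date is placed:

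- **Day missing:** for example, mid-month.
- **Month missing:** for example, the midpoint of the possible interval.
- **Bounds in both cases:** no earlier than the last date known alive (for a death) or progression-free (for a progression), and no later than the cut-off.
- **Sensitivity:** repeat OS and PFS with the earliest possible dates, and report how many dates were placed by rule.

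Other conventions would serve; the bounds and pre-specification matter most. Word this as an express exception in SAP 8.1.2 (including its last sentence), SAP 8.1.6, SAP 8.7 and protocol 8.6. Otherwise the new rule would contradict the general ban on imputation. Protocol 8.7 allows changes to the planned analyses through a protocol revision or an amended SAP.

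The cost is a few sentences, one derivation and a repeat run of two analyses. The downside is an assumed date, within a known interval, for a few patients.

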8.1.3 Baseline

Unless otherwise specified, baseline is defined as the last non-missing measurement taken prior to the date of initial ablation (Day 0) (including unscheduled assessments). Ultrasound and/or CT scan on Day 0 is taken prior to ablation, and is considered baseline (including unscheduled assessments).

Change from baseline will be defined as the difference between the post-baseline value at the point of interest and the baseline value.

8.1.4 Visit 2 Summaries, Retests, Unscheduled Visits

Visit 2 is split into 2 distinct phases: ablation (visit 2A) and post-ablation (visit 2B). Listings and summaries will be presented by phase of the visit, as appropriate.

In general, for by-visit summaries, data recorded at the scheduled visit will be presented. Unscheduled and reduced follow-up measurements will not be included in by-visit summaries.

Listing will include scheduled, unscheduled, retest.

8.1.5 Last Contact Date

The last contact date will be derived for subjects not known to have died at the analysis cut-off date using the latest date among the following applicable or available data:

- All visit dates, including examination/scan dates (e.g. laboratory, vital signs, NPRS pain, EORTC QLQ- HCC 18/C 30, ECG, ECOG, tumor imaging scan, tumor assessment)
- Medication/procedure dates (including ablation, concomitant medications/surgeries, therapies/procedures administered after study treatment discontinuation, etc.)
- Adverse event start and end dates

- Dates of protocol deviations
- Date of trial completion/discontinuation in [CRF form Subject Completion/Discontinuation]

8.1.6 Cut-off conventions

All available data will be included at the time of the cut-off date. Missing or partial dates (unable to compare) will also be presented, but no imputation for any date will occur except for partial adverse event dates as described in section *8.1.2*.

Adverse events and concomitant medications with no end date available by the cut-off date will be considered as ongoing events. If the start date is prior to / on the cutoff date, the end dates will be presented regardless if the end dates are post cut-off date or not. Ongoing events will be summarized for analysis using the cut-off date as the date of completion, with an indication that event is ongoing.

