coagulation dysfunction (bleeding tendency, prothrombin time [PT] was greater than normal control for 3~5 seconds, platelet count [PLT] was less than 50x10*fl., and the international normalized ratio [INR] was greater than 1.5). 8. Patient with renal failure and on renal dialysis. 9. Scheduled concurrent procedure other than MW ablation in the liver. 10. Pregnant or breast feeding. 11. Physical or psychological condition which would impair study participation. 12. Participation in any other interventional clinical study within 1 month before screening and concurrently during the study. 13. The patient is judged unsuitable for study participation by the investigator for any other reason. Planned recruitment period: approximately 8 months for 137 patients at 4 participating sites. Follow-up period: 36 months. Patients will be assessed for all AEs and SAEs for 30 days after any ablation procedure (original or additional); after 30 days post an ablation procedure through the end of the study, only SAEs will be reported. Categorical variables will be summarized descriptively by frequencies and associated percentages. Continuous variables will be summarized descriptively by number of patients, mean, standard deviation, median, minimum, and maximum. Confidence intervals will also be provided for procedure-related variables. The number and percentage of tumors achieving Technical Success will be summarized and a 95% confidence interval will be estimated. Technical Success will be evaluated based on the margin achieved after the first ablation and prior to any repeat ablations within the first 7 days. A similar summary will be provided for Technical Efficacy. This endpoint will be based on the scan obtained at Visit 3 and will count				

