10.2. Likelihood Analysis of Failure

In a prospective study in China, the rate of major complications (3.8% of patients) was low and no deaths occurred within 30 days of ablation. To date, more than 400 units of the Certus Microwave Ablation System and Accessories have been sold in the United States, Canada, European Union, and Singapore, where thousands of patients have been successfully treated. In recent years, MW ablation is gaining momentum in China. Because of this growing popularity of MW, failure to meet total enrolment (137 patients) in approximately 8 months, as stipulated by the protocol, is unlikely. Also, because of the low rate of major complications in patients who have been treated with MW ablation, it is unlikely that the study will be discontinued because of safety concerns.

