8.5.1 Adverse Events

An AE is defined as any undesirable clinical occurrence in a patient. An AE does not necessarily have a causal relationship with the study medical device. AEs will be recorded since date of informed consent signature until 30 days after any ablation procedure except SAEs with 36 months follow-up period.

Adverse events will be summarized by System Organ Class (SOC) and Preferred Term (PT) and broken down further by maximum severity and relationship to study device or procedure. Number (n) and percentage (%) will be presented with the percentage calculated relative to the total number of subjects in the FAS/SAF as following:

- AE Overview (subgroup by initial only and repeat ablation, run-in analysis set and full analysis set, and total count of safety analysis set)
- AE by SOC and PT
- Procedure related AE by SOC and PT
- Study device related AE by SOC and PT
- Serious AE by SOC and PT
- Procedure related serious AE by SOC and PT
- Study device related serious AE by SOC and PT
- AE by SOC, PT, and maximum severity
- AE by SIR and PT
- AE listings will be prepared. Information including SIR, PT, relationship with device/procedure, seriousness, severity, AE start and end date, intervention/treatment taken, outcome of AEwill be presented.

AEs will be coded using MedDRA Version 19.0 or higher.

Procedure-related AE

A procedure-related AE is an adverse event related to the study procedure. The relationship with study procedure is recorded as "Unlikely related", "Possibly related", "Probably related", and "Causal relationship".

Device-related AE

A device-related AE is an adverse event related to the use of the study device. The relationship with study device is recorded as "Unlikely related", "Possibly related", "Probably related" and "Causal relationship". Events marked with missing relationship with study device is considered as device-related AE.

Serious Adverse Event (SAE)

A Serious Adverse Event is any AE that:

- Resulted in death: An AE that resulted in the patient's death.
- Life-threatening illness or injury: The patient was at imminent risk of dying at the time of the AE.
- Permanent Impairment: An AE that resulted in permanent impairment of a body function or permanent damage to a body structure.

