8.6 Plans for Interim Analysis

There will be 2 interim analyses.

The first interim analysis will occur after all enrolled subjects have completed the 1month visit and is intended to provide an initial estimate of device effectiveness for Technical Success and Technical Efficacy as well as to summarize the perioperative out to 1-month post-operative safety profile of subjects undergoing microwave ablation.

The second interim analysis will occur after all enrolled patients have completed the 12-month visit and will include a summary of local tumor progression rates as well as safety through one year.8.7 Handling of Missing Data

There will be no imputation of data for early terminated subjects or for enrolled subjects who do not provide a measurement at a given visit.

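### Interim safety summaries labelled 1-month and one-year have no per-subject onset limit, so their crude SAE percentages would cover about 1-9 and 12-20 months of follow-up

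*SAP*

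**What the plan says.** On timing, SAP 8.6 states: "The first interim analysis will occur after all enrolled subjects have completed the 1month visit". Its safety purpose is to "summarize the perioperative out to 1-month post-operative safety profile of subjects undergoing microwave ablation". For the later look, "The second interim analysis will occur after all enrolled patients have completed the 12-month visit", and it "will include a summary of local tumor progression rates as well as safety through one year". Protocol 8.1 describes both analyses in the same terms.

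On which data enter, SAP 8.1.6 states: "All available data will be included at the time of the cut-off date". The only test it applies to an event's start date is against that calendar date. The SAP does not say how the date is set. Protocol 8.6 uses another calendar date, the interim database lock, to censor subjects who are still on study.

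On the summary measure, SAP 8.5.1 reports numbers and percentages of subjects, with the "percentage calculated relative to the total number of subjects in the FAS/SAF". It sets no limit on onset. Protocol 8.1 also requires AE rates per patient-year and per number of ablations. SAP 8.5 lists neither.

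On collection, protocol 7.1.7 and SAP 8.5.1 gather all AEs until 30 days after any ablation, original or repeat, and SAEs throughout the 36 months. Protocol 7.2.2 allows re-ablation for recurrence at any time.

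On accrual, the protocol synopsis gives: "Planned recruitment period: approximately 8 months for 137 patients at 4 participating sites". Protocol 10.2 relies on the same figure.

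**The concern.** When the last subject completes Month 1, the first subjects have been followed for much longer. If every SAE up to the calendar cut-off is counted over all FAS or SAF subjects, the result is a percentage with no defined time frame. It would rise with slower recruitment even if the device and the patients were unchanged.

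Three consequences follow.

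- The first interim's stated safety purpose, the peri-operative to 1-month profile, is not met by such a percentage.
- Protocol 8.4 judges performance in the context of other therapies, and protocol 4.1.1 and 10.2 cite a series with no deaths within 30 days. A percentage accumulated over 1-9 months is not on the same footing as a 30-day figure.
- The AE overview in SAP 8.5.1 shows run-in and full-analysis columns. The 125 main-phase subjects are enrolled after the run-in phase, so run-in subjects tend to have the longest follow-up. Their SAE percentage could look worse for that reason alone, which would confuse any reading of a learning curve.

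**Working it through.** **Sample size (SAP 7).** 100 / (1 − 0.20) = 125, and 125 + 3 × 4 = 137. This reproduces the plan's figure. The documents state no follow-up range at either interim, so that has to be derived.

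**Follow-up at each interim.** Let L be the month the last subject has reached and A the accrual time. Follow-up then runs from L to L + A. With uniform accrual (assumed) its mean is L + A/2, and the share of patient-time beyond the label is (A/2) / (L + A/2). Dropout and death are ignored.

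| | Interim 1 (L = 1) | Interim 2 (L = 12) |
|---|---|---|
| Range, A = 8 | 1 to 9 months | 12 to 20 months |
| Mean | 1 + 4 = 5 months | 12 + 4 = 16 months |
| Share beyond label | 4/5 = 80% | 4/16 = 25% |
| Upper end, A = 6 to 12 | 7 to 13 months | 18 to 24 months |

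The visit windows move the upper ends slightly: 9 + 7/30.4375 = 9.2 months and 20 + 14/30.4375 = 20.5 months. Any delay between the last visit and the cut-off adds to this.

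**Which outputs are affected.**

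| Output | Covers time beyond the label? |
|---|---|
| SAE percentages (SAP 8.5.1) | Yes; collection continues to 36 months |
| AEs after late re-ablations | Yes; each ablation opens a new 30-day window |
| ECOG shift to worst post-baseline score (SAP 8.5.4) | Yes; no time limit |
| Non-serious AEs after a single ablation | No; collection stops at 30 days |
| By-visit summaries (SAP 8.1.4) | No; scheduled-visit data only |
| Technical Success, Technical Efficacy | No; fixed at Visits 2B and 3 |

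**Size for SAEs.** The documents give no SAE hazard, so I assume a constant background hazard h of 0.5% to 2% per month. The mean excess follow-up is A/2 = 4 months, so to first order the excess is 4 × 0.5% = 2 points to 4 × 2% = 8 points.

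Without the linear approximation, the percentage to cut-off is 1 − (e^(−hL) − e^(−h(L+8))) / (8h), against 1 − e^(−hL) with a per-subject limit:

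| h per month | Interim 1: limited → to cut-off | Excess | Interim 2: limited → to cut-off | Excess |
|---|---|---|---|---|
| 0.5% | 0.5% → 2.5% | 2.0 points | 5.8% → 7.7% | 1.9 points |
| 2% | 2.0% → 9.4% | 7.4 points | 21.3% → 27.3% | 6.0 points |

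Expressed another way, an assumed one-year SAE risk of 10% gives 0.9% against 4.3% at the first interim (1.1 against 5.3 of 125 subjects). At the second it gives 10.0% against 13.1% (12.5 against 16.4 of 125). Over assumed one-year risks of 5% to 30%, the ratio is 4.7 to 5.0 at the first interim and 1.26 to 1.32 at the second. These ratios apply to background SAEs only. A cluster of peri-procedural SAEs would be counted under either rule and would pull the ratio towards 1, so the excess in points is the safer figure to quote.

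**The case against.** The strongest reply is that SAP 8.1.6 is a general convention, mostly about partial dates and ongoing events, while SAP 8.6 is specific to the interims and sets their scope. If the specific section governs, the limit is already implied. That reading is open, and it means the SAP does not announce an intention to mix follow-up times. But 8.6 states a purpose and gives no counting rule, whereas 8.1.6 is a rule. Two programmers could produce different SAE tables from this text.

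A second reply is that the protocol defines the safety endpoint as reported at each analysis and cumulatively (7.1.2 and 7.1.7). This stands. Cumulative reporting at an interim has protocol support, so later SAEs should not be confined to listings.

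A third is that little depends on the interims. The study is descriptive, neither look is used to stop it, and the final analysis is unaffected. AE listings carry start dates, so early events could be recovered by hand. This limits the importance of the point but does not make the labelled percentages right.

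Two stronger inferences are tempting and should be resisted.

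- A reader might infer that whole interim reports mix follow-up times. The table of outputs above shows that most safety data after a single ablation, and the two technical endpoints, have fixed windows.
- A reader might take the cited one-year survival of 91.2% and compute −ln(0.912)/12 × 4 × 137 = 4.2 extra deaths in the 1-month tables. The documents do not support that use. Under protocol 14.2, death itself is not reported as an SAE and its cause is exempt when it is progressive disease. SAP 8.5.2 sends deaths to a listing. An all-cause figure therefore does not measure inflation of the SAE percentages.

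**Conclusion.** The point holds for crude SAE percentages, AEs after late re-ablations and the worst post-baseline ECOG shift. As written, SAP 8.1.6 and 8.5.1 do not deliver the windows named in SAP 8.6, and nothing in either document resolves the conflict. The follow-up ranges of about 1-9 and 12-20 months rest only on the planned 8-month accrual and widen if recruitment is slower. The excess of about 2-8 points at the first interim is hypothetical: it needs uniform accrual and an assumed constant SAE hazard of 0.5-2% per month. Disease progression is not reported as an SAE (protocol 14.2), which may put the true hazard towards the lower end or below it. The change is worth making because the labelled percentages would otherwise depend on recruitment speed and the remedy is small. It does not threaten the final analysis.

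**What to change.** In SAP 8.6, define how each interim cut-off date is set.

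In SAP 8.6 and 8.5.1, limit the labelled interim AE and SAE tables to events with onset by each subject's Month 1 limit (first interim) or Month 12 limit (second interim), with a fixed day limit where the visit is missing. Apply the same limit to the worst post-baseline ECOG shift in 8.5.4. State the day limit as days elapsed since the ablation date, because SAP 8.1.1 numbers the ablation day 0 while the formula in 8.1.2 gives 1.

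Beside these, show all events to cut-off in a separate table labelled cumulative, with the patient-year and per-ablation rates that protocol 8.1 requires. State in 8.1.6 that its rule governs the cumulative tables and the listings.

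The cost is a few sentences in the SAP, an onset-date filter, and one extra set of interim tables. No data are lost and data collection does not change.
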